1. Hypothesis and Specific Aims

Overarching Hypothesis: Insulin signaling is a critical neurobiological substrate of anhedonia in mood disorders

Specific Hypotheses: In individuals with mood disorders, objective and self-reported measures of anhedonia and reward behaviors are associated with alterations in insulin signaling-related molecular, cellular and neural substrates. Considering the role of insulin in the regulation of energy expenditure, we primarily hypothesize that individuals with mood disorders will display decreased willingness to make effort for rewards, relative to healthy controls; and that this abnormality will be associated with:

- a) Molecular: Differential gene and protein expression of the metabolic (i.e. PI3K/Akt) and mitogenic (i.e. Ras/MAP kinase) components of the insulin signaling pathway, as well as with components of reward-related processes (i.e. dopamine receptors and transporter)
- b) Physiology: Reduced peripheral sensitivity to insulin and corresponding metabolic correlates, including increased body mass index and dyslipidemia (i.e. peripheral insulin resistance)
- c) Neural Circuits: Diminished response to insulin in cortico-striatal networks (i.e. brain insulin resistance)

Overarching Aim: To determine the role of insulin signaling on the neurobiological substrates subserving anhedonia within individuals with mood disorders.

Specific Aims:

- a) Molecular: Assessment of components of the insulin cascade, as well as of anhedonia and reward-related processes, using a proteomics and gene expression approach;
- b) Physiology: Measurement of peripheral sensitivity to insulin and metabolic correlates, including body mass index and dyslipidemia;
- c) Neural Circuits: Evaluation of the insulin sensitivity of prefrontal (e.g. prefrontal cortex) and striatal (e.g. nucleus accumbens, ventral tegmental area) networks in the resting-state and during an effort-based decision making test, using acutely administered intranasal insulin and functional magnetic resonance imaging (fMRI);
- d) Behavioral: Measurement of willingness to make effort for rewards, as well as of other components of reward response and anhedonia, using validated behavioral tasks and clinical scales (e.g. Snaith-Hamilton Pleasure Scale SHPS).

2. Background and Rationale

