- 2. Diagnosis of possible or probable AD, MCI, or any other dementia
- 3. History of neurological disorder, or evidence of neurologic or other physical illness that could produce cognitive deterioration
- 4. Substance use disorder within 3 months before screening or a positive baseline toxicology screen
- 5. Presence of clinically unstable general medical illness
- 6. Pregnancy or breastfeeding
- 7. MRI contraindications

Inclusion criteria (healthy controls):

- 1. Age 18-50
- 2. A written, voluntary informed consent prior to study enrollment

Exclusion criteria (healthy controls):

- 1. Use of insulin and/or oral hypoglycemiants, due to its confounding effects
- 2. Presence of any current or lifetime psychiatric or neurological conditions
- 3. Substance use disorder within 3 months before screening or a positive baseline toxicology screen
- 4. Presence of clinically unstable general medical illness
- 5. Pregnancy or breastfeeding
- 6. MRI contraindications

Study Procedures: Single-dose, randomized, controlled, double-blinded, cross-over study (50 participants)

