This procedure is repeated until the required number of nasal spray bottles has been prepared. Once completed, the nasal spray bottles are wiped with 70% isopropyl alcohol soaked gauge and removed from the laminar flow hood and appropriately labeled.

Both active and placebo nasal spray bottles are kept separate from each other and a worksheet will be completed to document information, including date of preparation, batch #, expiry date, drug name and strength. The IV certified pharmacy technician who has prepared the dose is responsible for completing the documentation and will be affixing the labels identifying what was prepared. The labels, at a minimum, will contain information regarding the lot #, strength, date of manufacture, expiry date, and storage conditions. All of this will be verified by a pharmacist.

Labeling

All labels will contain product name, volume, protocol number, investigational drug warning, dosage instructions, storage conditions, lot number, expiration date, and the pharmacy name.

Storage

Please refer to the pharmacy manual for information on storage.

Study Medication Administration

This will be a single-dose, randomized, double-blinded, cross-over study involving intranasal insulin/placebo solution.

Designated pharmacy staff will dispense study medication, in a double-blind manner, according to the randomization code specific to each subject and dosing period.

Details regarding intranasal insulin and diluent can be referred to in the pharmacy manual.

The investigator and/or designee will instruct the study participant on how the intranasal insulin/placebo spray should be administered. Each study participant is to receive a single dose of Humulin R 160 U / placebo.

- Given:
 - The nasal spray bottles provide a deliverable volume of 0.1 mL/spray.
 - o Humulin R insulin will be sourced as 100 units/mL in a vials of 10 mL from Eli Lilly.
 - o Diluent will be sourced as 10 mL/vial from Eli Lilly.
- Each spray will offer:
 - o 0.1 mL (i.e., 10 units) of Humulin R insulin
 - o 0.1 mL of diluent (to serve as placebo)
- To obtain a dose Humulin R 160 U / placebo
 - o 16 sprays (0.1 mL/spray) are to be given per dose

- o This works out to 16 sprays split between each nostril such that each nostril receives 8 sprays.
- The sprays will be administered between alternating nostrils.

Given this is a crossover study, the study participants will receive a total of two doses in this study. The time between 2 doses is one week.

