4.3 Disposition of Used/Unused Product

Please refer to the pharmacy manual for information on the disposition of used/unused product.

5. Methods of Assigning Subjects to Treatment Groups

Please refer to the pharmacy manual for information on the methods of assigning subjects to treatment groups (i.e. randomization, and blinking/masking).

6. Analytic Plan, Power Analysis and Approach to Potential Challenges

Initial data analyses will inspect socio-demographic and clinical group differences as well as correlations between clinical and biological variables and specified behavioral measures. Clinical or demographic variables demonstrating a correlation with both biological and behavioral measures, will be assessed as potential confounders⁸². The EEfRT behavioral data will be analyzed using generalized estimating equation (GEE) models, according to previous studies^{30,33}. For the assessment of associations between the remaining behavioral measurements and biometric data, we will use generalized linear models, due to its greater flexibility and ability to analyze data with non-normal distributions. Group (mood disorders vs. non-psychiatric) effects will be analyzed, with age, gender, and other relevant covariates included in the models. Special considerations will be given to smoking and use psychotropic medications, given its potential effects of both reward processes and insulin signaling.

Mediation and moderation models will be assessed using regression-based, bias-corrected bootstrap tests⁸³. The main objective is to test whether there is a mediated effect of X (i.e. mood disorders) on the outcome Y (i.e. anhedonia and reward behavior) through M (i.e. insulin signaling and dopamine metabolism). If appropriate, moderated mediation models (conditional process analysis) will be used to test whether the mediation effect was contingent on a moderating variable W (e.g. obesity, medications). This method uses bootstrapping to determine bias-corrected (asymmetric) 95% confidence intervals for the indirect effects⁸⁴. Bootstrapping methods have been recently advocated, as they are based on random sampling of the data and do not make assumptions about the shape of the sampling distribution; they are also more powerful and allow for the construction of more accurate confidence intervals, relative to normal theory methods⁸³.

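### Neither exclusion list covers nasal obstruction or intranasal medicines, although the exposure is 16 nasal sprays and a small response is read as brain insulin resistance

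*Combined protocol and SAP*

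**What the plan says.** Section 3 gives separate exclusion lists for patients and healthy controls. Both cover glucose-lowering drugs, neurological conditions, substance use, pregnancy or breastfeeding, and MRI contraindications. The patient list adds dementia, and the control list adds psychiatric conditions. Two entries come closest to this point, and both appear in both lists: "Presence of clinically unstable general medical illness" and "Use of insulin and/or oral hypoglycemiants, due to its confounding effects". No entry concerns the nose, the sinuses or products taken by the nasal route.

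Section 4.1 (Study Medication Administration) makes the exposure entirely nasal: "16 sprays (0.1 mL/spray) are to be given per dose", that is, "16 sprays split between each nostril such that each nostril receives 8 sprays".

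Section 1, hypothesis (c), states the imaging expectation as "Diminished response to insulin in cortico-striatal networks (i.e. brain insulin resistance". Section 3 (Neural Circuits Assessment) uses the response to the intranasal challenge as the proxy for insulin activity in the chosen regions. Section 6 compares insulin with placebo within each participant, then compares patients with controls, and relates imaging to behavioral and biometric measures.

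**The concern.** A person with stable chronic rhinosinusitis, nasal polyps, a structural obstruction or a daily nasal spray can meet every criterion and be dosed. If little insulin gets past the nasal cavity, the insulin-placebo difference is small. The plan's own definition reads that as brain insulin resistance. Nothing in the planned data separates failed delivery from a brain that responds weakly.

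The crossover does not protect against this. It removes stable differences between people that act equally in both periods. Poor delivery acts only where there is insulin to deliver, so it comes straight off the contrast. At stake are the sensitivity of the imaging comparison and the meaning of each participant's response when it is related to anhedonia, effort and metabolic measures.

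**Working it through.** **1. The plan's dose figure.** Section 4.1 gives 16 sprays per dose, 0.1 mL per spray ("The nasal spray bottles provide a deliverable volume of 0.1 mL/spray") and 100 units/mL ("Humulin R insulin will be sourced as 100 units/mL in a vials of 10 mL from Eli Lilly"). So 16 × 0.1 mL = 1.6 mL, and 1.6 mL × 100 units/mL = 160 U, with 16 / 2 = 8 sprays per nostril. The stated 160 U reproduces. No other route contributes.

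**2. Model.** Let D be the true mean insulin-minus-placebo response in SD units of the within-person difference, f the share of a group with impaired delivery, and d the fraction of response kept in those affected. The observed group mean is D × [1 − f(1 − d)]. The documents give no value for D, f or d, so every value below is an assumption. The group size of 25 is from section 3. The enrollment figure of 150 in section 6 belongs to the mediation power calculation and is not used here.

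**3. Dilution with equal impairment (d = 0).**
- f = 15% in both groups: the mean is 0.85D, a 15% loss.
- The sample needed to restore power grows by 1 / 0.85² = 1.38, so 50 participants do the work of 50 / 1.38 ≈ 36.
- With D = 0.5 in 25 patients (two-sided z-test at 0.05): 0.5 × √25 = 2.5 and power ≈ Φ(2.5 − 1.96) = Φ(0.54) ≈ 70%. After dilution, 0.85 × 2.5 = 2.125 and power ≈ Φ(0.165) ≈ 57%.
- f = 20% in both groups: 0.50 becomes 0.40 and 0.80 becomes 0.64, with no group gap.

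**4. Individual level.** A participant with impaired delivery shows dD instead of D. A participant with full delivery but only a fraction d of the normal brain response shows the same value. The error therefore enters the imaging association models, and the mediation models so far as the imaging response stands for insulin signaling, even when f is equal across groups.

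**5. False group difference with unequal impairment.** With the true response equal in both groups, gap = (f_patients − f_controls)(1 − d)D. The standard error is √(2/25) = 0.283, and the test is a two-sided z-test at 0.05.

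| Patients vs controls | d | Gap (D = 0.5 to 0.8) | False-positive rate |
|---|---|---|---|
| 20% vs 8% | 0 | 0.06 to 0.10 SD | 5.5% to 6.3% |
| 20% vs 8% | 0.5 | 0.03 to 0.05 SD | 5.1% to 5.3% |
| 30% vs 10% | 0 | 0.10 to 0.16 SD | 6.4% to 8.7% |
| 30% vs 5% | 0 | 0.13 to 0.20 SD | 7.3% to 10.9% |
| 40% vs 10% | 0 | 0.15 to 0.24 SD | 8.3% to 13.6% |

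**6. Existing safeguards.**
- Section 3 has a general comorbidity questionnaire and a record of current medications.
- The adverse-event section has staff ask about health problems at each visit.
- Section 6 leaves its list of confounders open.
- Plasma insulin and glucose are drawn at the spray and after the scan, but not as a delivery check. Section 3 itself says the route has no relevant effect on peripheral glucose.
- Table 1 has no nasal item.

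None of these is linked to a nasal exclusion, covariate or sensitivity analysis.

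**The case against.** A reader might infer that poor delivery will create a false deficit in patients, on the grounds that they smoke more, are more often obese, or are less healthy than volunteers. The documents do not support this.
- They give no prevalence of nasal disease and do not link it to mood disorder, smoking or obesity.
- Obesity is to be balanced against normal weight in the imaging subsample.
- Controls carry the same general-medical exclusion as patients. Their additional criterion is psychiatric, so nothing selects them for healthier noses.
- Smoking is measured as pack-years, and the plan says "Special considerations will be given to smoking and use psychotropic medications", which could adjust for part of any smoking-linked imbalance.

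Total delivery failure is also a harsh assumption when sprays alternate between both nostrils. A cold at a single visit falls on insulin or placebo according to randomized order, so it adds noise and not a systematic group bias. The comorbidity, medication and health-problem records may already capture some nasal conditions. Section 6 deliberately seeks a naturalistic sample, which argues against broad exclusions. The imaging response is one of several hypothesized correlates, and the primary behavioral measure is the effort task. Finally, the pharmacy manual is not among the documents. The protocol cites it for product details, storage, accountability, disposition, randomization and masking, so a nasal check there is unlikely but cannot be ruled out.

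These arguments remove most of the case for a false group difference. They do not answer dilution or individual misclassification, neither of which needs an imbalance. Nor do they supply a pre-specified use for whatever nasal information is recorded.

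**Conclusion.** The gap is real and worth closing, but it does not invalidate the trial. Neither exclusion list addresses the route of exposure, the plan's definition cannot tell failed delivery from a weak brain response, and the crossover does not remove the problem.

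The expected harm is loss of sensitivity, proportional to the share of participants with failed delivery (15% of the effect at an assumed 15% with total failure), plus misclassification in the participant-level models. A spurious patient-control difference is conditional on unequal impairment. If that existed, the effect on the error rate would be small to modest: about 5.5-6.3% instead of 5% at 20% versus 8%. It would be larger only under more extreme imbalances, and smaller if delivery were partly preserved. All rates and effect sizes here are assumptions. Only the dose arithmetic and the 25 per group come from the documents.

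**What to change.** - Add one line to both exclusion lists: current nasal or sinus disease or structural obstruction that impairs nasal delivery, and current use of intranasal medicines. Wording it by impaired delivery avoids excluding every past nasal operation and keeps the sample close to the naturalistic one intended.
- Record nasal status with one pre-spray question at Visits 2 and 3, and add it to Table 1. The MRI questionnaire is already repeated at those visits in the same way.
- Pre-specify in section 6 a sensitivity analysis of the insulin-placebo contrast and of the group-by-condition comparison, excluding participants with nasal symptoms at a spray visit.

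Whether a visit is postponed for acute symptoms is for the sponsor to decide. Any such rule must be reconciled with the one-week interval between doses in section 4.1.

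The cost is a few screen failures, one question per spray visit and a slightly narrower sample. The sensitivity analysis will have fewer participants, so it should be read beside the main result and not in place of it.

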Screening and Baseline Assessment: Patients and healthy controls will first meet, in-person or virtually, with a staff psychiatrist for a clinical consultation or a research team member, respectively. After obtaining consent and if inclusion criteria are met, a medical comorbidity questionnaire will be administered to screen for concurrent and lifetime medical conditions. Participant's demographic characteristics and current medications, as well as lifetime psychotropic medications received will be recorded. We will also assess dietary intake with the Diet History Questionnaire III (DHQ III); smoking, by questioning number of cigarettes smoked per day, age when smoking started, and quitting date, if applicable, to calculate a smoking pack-year history; physical activity using the International Physical Activity Questionnaire (IPAQ); and alcohol and/or substance abuse. In addition, we will assess demographics, socioeconomic status, medical history, and family psychiatric history; childhood trauma history with the Childhood Trauma Questionnaire (CTQ) will also be assessed. Participants will also be asked to complete an MRI screening questionnaire to ensure that they have no contraindications. The following self-reported measures will be carried out: Perceived Deficits Questionnaire-Depression (PDQ-D), Sheehan Disability Scale (SDS), UCLA life Stress (Episodic), DeJong Gierveld Loneliness Scale, and Pittsburg Sleep Quality Index (PSQI) (Table 1).

When in-person visits are possible, participants will complete a urine drug screen. Female participants will be asked to do blood work to confirm they are not pregnant.

Physiological Assessment: Anthropometric (i.e. BMI, waist-hip ratio) and metabolic measurements (i.e. fasting glucose, fasting insulin, glycated hemoglobin, lipids and HOMA-IR) will be completed at each study visit (1-3). In addition, physical activity and energy expenditure will be measured using an accelerometer. Participants must wear the accelerometer at all times for one week and return it upon Visit 3 for data collection and analysis. Additionally, a heart rate monitor device will be connected to the accelerometer that will monitor heart rate variability over one day of the week that the subjects wear the accelerometer.

Laboratory Assessment:

Routine: the following laboratory tests will be completed:

Triglycerides
Total Cholesterol
Insulin
Glucose
HbA1c
C-Peptide
IGF-1
TSH
Free T4
Free T3
C-Reactive Protein
hCG

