After screening and baseline assessment, participants will receive a crossover treatment assignment of either insulin or diluent followed by an MRI scan, with a washout period of 1 week. Therefore, participants will receive a total of 2 MRI scans throughout the course of the study- one following the first treatment, and one following the second treatment. The subsample will be enriched for the presence of self-reported anhedonia, using a score of greater than 2 on the SHPS as a cut-off, which provides the best discrimination between "normal" and "abnormal" level of hedonic tone⁸¹. This subsample will also have equal representation of normal weight and obese participants.

To proxy insulin activity within pre-selected brain regions, we will use a provocation paradigm, involving the administration of exogenous intranasal insulin, based on the published work of other research groups research groups Activation of brain regions will be assessed during the resting state and task-based reward paradigm (i.e. EEfRT), following an intranasal administration of either 160 units of intranasal insulin or diluent (insulin and placebo will be prepared as nasal sprays), in a randomized, double-blinded, cross-over design. Please refer to the pharmacy manual for randomization details. A hypothesis-driven region of interest approach will be used to investigate initially the striatum and the medial PFC (mPFC). Willingness to make effort for rewards will be measured with the EEfRT³³. Briefly, participants have to select between an easy and a hard task. Both tasks involve pressing a key for a predetermined amount of time. The hard task offers more money (variable amounts), but is harder and takes twice as long. Participants make their selection knowingly under different win probabilities (i.e. they might not win money even if they are successful if the win probabilities are low). This task will measure proportions of hard-task choices with varying probabilities of reward and reward magnitudes. To provide stable estimations, the fMRI task will be conducted in three runs⁷³.

Table 1

Assessment	Baseline (V1)	First Spray (V2)	Second Spray (V3)		
General Information					
Demographics	✓				
Questionnaire					
Medical Comorbidity	✓				
Questionnaire					
Family Psychiatric	✓				
History					
Questionnaire	,				
SES Questionnaire	√				
MRI Questionnaire	✓	✓	✓		
Anthropometric Measures					
Height (ft)	✓				
Weight (kg)	✓	✓	✓		
Blood Pressure	✓	✓	✓		
(mmHg)					

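### The baseline drug screen is conditional and unscheduled, and hCG is scheduled only at Visit 1, so neither exclusion is tied to the visits at which participants are dosed and scanned

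*Combined protocol and SAP*

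**What the plan says.** The exclusion lists in section 3 (Design and Methodology) are the same for patients and controls on two items. The drug item reads "Substance use disorder within 3 months before screening or a positive baseline toxicology screen" (item 4 for patients, item 3 for controls). The pregnancy item reads "Pregnancy or breastfeeding" (item 6 for patients, item 5 for controls).

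Screening and Baseline Assessment sets out how participants enter: "Patients and healthy controls will first meet, in-person or virtually, with a staff psychiatrist for a clinical consultation or a research team member, respectively". On testing it says "When in-person visits are possible, participants will complete a urine drug screen" and, in a separate sentence, "Female participants will be asked to do blood work to confirm they are not pregnant". Only the first of these two sentences carries the in-person condition.

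On sequence, Neural Circuits Assessment says "After screening and baseline assessment, participants will receive a crossover treatment assignment of either insulin or diluent followed by an MRI scan". Sprays and scans fall at V2 and V3. Study Medication Administration (section 4.1) puts the two doses one week apart. The interval from V1 to V2 is not stated.

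Table 1 ticks hCG at V1 only and has no row for a urine drug screen. Separately, Physiological Assessment says that anthropometric measures, including waist-hip ratio, "will be completed at each study visit (1-3"), whereas Table 1 ticks waist/hip circumference at V1 only.

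**The concern.** An exclusion for a positive baseline screen works only if every participant has a screen and the result is known before exposure. As written, the test depends on visit logistics, and a participant who was never tested has no positive result and so passes the criterion.

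The primary behavioural measure is effort-based choice on the EEfRT, and the lead hypothesis is a difference between patients and controls on it. The protocol's own exclusion treats a positive screen as disqualifying. If completeness of testing varies with mode of contact, and mode of contact differs between groups that are first seen by different staff, the group contrast could be affected. The within-person comparison of insulin with placebo is less exposed, provided drug use is stable across the two visits.

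The pregnancy exclusion is a safety rule. Its only scheduled test comes before both exposures by an interval that the protocol does not limit.

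**Working it through.** The plan gives no figure to reproduce, so the check is a comparison of the eligibility criteria, the screening text, the schedule and the dosing-day procedures.

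**Drug screen**

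1. Criterion: a positive baseline result excludes, in both groups.
2. Screening text: the test is done when in-person visits are possible. No visit number or deadline is given.
3. Laboratory Assessment list: 12 tests, none of them a drug screen.
4. Table 1: scheduled drug screens at V1 = 0, V2 = 0, V3 = 0, because there is no row.
5. Dosing-day checks named before imaging: glucose and cardiovascular vital signs, plus an MRI questionnaire ticked at all three visits whose content is not given.
6. Result: no statement requires a drug-screen result before the first spray.

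**Pregnancy test**

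1. Criterion: pregnancy excludes, in both groups.
2. Screening text: blood work for female participants, not conditional on visit mode.
3. Table 1: hCG at V1 = 1, V2 = 0, V3 = 0. The other 11 laboratory rows are ticked at V1, V2 and V3.
4. Age of the result at exposure: let x be the days from V1 to V2. The result is x days old at V2 and x + 7 days old at V3. The documents do not give x. Purely as an illustration, if x lies between 0 and 28 days, the result is 0 to 28 days old at V2 and 7 to 35 days old at V3.
5. Blood is drawn at V2 and V3 both for the laboratory panel and around the spray and scan, so a further assay needs no new visit.

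**Scale**

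The Study population paragraph gives 25 patients and 25 controls. One undetected positive is 1/25 = 4% of a group. The documents give neither the share of participants met virtually nor a rate of positive screens, so no expected count can be derived.

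**Waist and hip**

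Physiological Assessment has waist-hip ratio at visits 1 to 3; Table 1 has the circumferences at V1 only. The two statements disagree.

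**The case against.** The best counter-argument is that only the first meeting may be virtual. V1 as scheduled includes blood tests, weight, blood pressure and waist/hip circumference, so it has in-person components, and V2 and V3 must be in person for the spray and the scan. On that reading, the conditional sentence merely defers the urine test to the first in-person visit, and every dosed participant has one. This is a plausible intention, but the text does not state it, and a test done at V2 with no rule that its result precede the spray would still not enforce a baseline exclusion.

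Absence from Table 1 is also weak evidence by itself. The table omits other planned items, such as smoking history and the cytokine assays. The drug criterion refers to a baseline screen, so a dosing-day drug test was never promised. The substance use disorder half of the criterion does not depend on urine. These points stand. The finding rests on the conditional wording, the missing schedule entry and the missing deadline taken together.

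On pregnancy, the exclusion is checked once and unconditionally, and the repeated MRI questionnaire may ask about it. Its content is not shown, so it can neither be relied on nor dismissed. What remains is a gap in timing.

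**Conclusion.** The concern holds as a statement of what the protocol permits. A participant could be dosed and scanned without the drug exclusion having been tested, and the hCG result may be of any age at V2 and is a week older at V3. The drug limb is the stronger of the two. No sample size, power or alpha figure changes, and the effect on the group contrast cannot be quantified from the documents.

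Four stronger readings are tempting and are not supported:

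- **That the drug exclusion cannot be applied, or that the share never screened equals the share met virtually.** A virtual first meeting is not a virtual V1, and later visits are in person. Any expected number of missed positives would only multiply assumed rates.
- **That pregnancy goes unchecked.** hCG is planned at V1 regardless of how the first meeting is held.
- **That measuring height only at V1 misclassifies BMI or the weight strata.** Adult height is effectively constant, weight is taken at all three visits, and nothing provides for self-reported height.
- **That the waist/hip mismatch bears on eligibility.** It is a minor inconsistency, separate from drug and pregnancy screening.

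**What to change.** Reconcile the exclusion criteria, the screening text and Table 1:

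1. Make the urine drug screen unconditional and state that its result is required before the first spray. V2 is in person in any case, so a participant not tested by then can be tested there.
2. Add a toxicology row to Table 1 at the visit or visits chosen.
3. Tie verification of the pregnancy exclusion to the dosing and scan visits, using blood already drawn where the result can be available in time. The permitted age of a result, and whether the check is repeated at V3, are for the sponsor and investigator to set; no number of days is proposed here.
4. Correct either Physiological Assessment or Table 1 so that they agree on waist/hip.

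The cost is a wording change, a urine test, a few added assays and an occasional screen failure on the day of V2. Sites will also need to allow for assay turnaround before the spray.
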